1. INTRODUCTION

1.1 DISEASE BACKGROUND

Worldwide, colorectal cancer (CRC) is the third most common cancer (1,360,602 new cases in 2012), accounting for 10% of all cancers (not including non-melanoma skin cancer) and an estimated 693,933 deaths (8.5% of the total number of cancer deaths; the fourth most common cause of cancer deaths) (1). Almost 55% of new cases occur in more developed regions. In Europe, there were 447,000 new CRC cases and 215,000 deaths (12% of all cancer deaths) in 2012 (2). The National Cancer Institute (NCI) estimates 134,490 new CRC cases and 49,190 deaths (8% of all cancer deaths) in the U.S. in 2016 (3).

The median age at diagnosis is 68 years, and 90% of cases are diagnosed in those over 50 years of age. The lifetime risk for CRC is 6% in average-risk persons living in the U.S. The CRC-related 5-year survival rate is 65%. Approximately 20–25% of patients present with metastases (metastatic CRC [mCRC]) at initial diagnosis and almost 50% of the remainder will subsequently develop metastases, contributing to the high mortality rates reported for CRC. The overall prognosis of patients with mCRC is poor, with five-year survival in the 5–8% range. However, recent chemotherapeutic regimens combined with targeted agents have significantly improved their two-year survival.

For patients with non-curable mCRC, combination chemotherapy including oxaliplatin-based and irinotecan-based regimens remains standard for first-line and second-line therapies. For patients with wild-type KRAS tumors, cetuximab (an epidermal growth factor receptor inhibitor) is a common option for third-line therapy, improving median survival from 4.8 to 9.5 months when compared with supportive care alone (4). When 5-fluorouracil (5-FU) was the only active agent, overall survival (OS) was approximately one year. There are now eight different classes of drugs with significant antitumor activity in mCRC and patients routinely live longer than two years:

- Fluoropyrimidines (FP) (including 5-FU, which is usually given with leucovorin, capecitabine, S-1, and tegafur plus uracil).
- Irinotecan.
- Oxaliplatin.
- Cetuximab and panitumumab, two monoclonal antibodies directed against the epidermal growth factor receptor (EGFR).
- Bevacizumab, a monoclonal antibody targeting vascular endothelial growth factor (VEGF).
- Aflibercept, a recombinant fusion protein consisting of VEGF binding portions from the human VEGF receptors 1 and 2 fused to the Fc portion of human immunoglobulin G1.
- Regorafenib, an orally active inhibitor of angiogenic tyrosine kinases (including the VEGF receptors 1 to 3), as well as other membrane and intracellular kinases.
- Trifluridine-tipiracil (TAS-102), an oral cytotoxic agent that consists of the nucleoside analog trifluridine and tipiracil, which inhibits trifluridine metabolism and has antiangiogenic properties.

A median OS of 18.2 months in first-line mCRC patients is now reported with combinations of cytotoxic and biological therapies (5). Because OS may be prolonged by second- and subsequent-line therapies, exposure to all available treatment options at some stage (rather than in a particular order) may be more important so choosing an

appropriate treatment approach remains complex with several open questions and the need for new drugs as the underlying biology becomes better known and understood (6).

The best way to combine and sequence these agents is not yet established, and the goals of chemotherapy in this setting differ according to clinical scenario: for non-resectable disease in patients without symptoms, induction of a tumor response is not as important as is delaying tumor progression as long as possible. Systemic 5FU-based chemotherapy produces meaningful improvements in median survival and progression-free survival (PFS) compared with best supportive care (BSC) alone. These benefits are most pronounced with regimens containing irinotecan or oxaliplatin in combination with FU, which represent the mainstay of advanced and metastatic CRC chemotherapy. Consequently, when patients with advanced or metastatic CRC have received prior FP, irinotecan and oxaliplatin -based regimens (in addition to any ad hoc therapy targeting EGFR, and/or VEGF, according to tumor characteristics), new agents within clinical trials are warranted.

[figure not shown]
1.2 INFORMATION ON STUDY DRUG

The drug substance (DS) PM060184-CD is a mixture of PM060184 and 2-hydroxypropyl-β-cyclodextrin:

Chemical Name (IUPAC)	(1Z,4S,6Z)-1-((3S)-8-((2S)-5-methoxy-6-oxo-3,6-dihydro-2H-pyran-2-yl)-6-methylnona-2,4,6-trienoyl]-3-methyl-L-valyl)amino)octa-1,6-dien-4-yl carbamate
Other name	PM060184 HPβCD

The structural and molecular formulas of PM060184 are shown in [Figure 1](#).

Figure 1. Chemical structure of PM060184.

- the hematopoietic system, characterized by a moderate to severe reticulopenia, leukopenia, and thrombocytopenia, atrophy of the thymus, decrease in bone marrow cellularity (mainly in rats), and extramedullary hematopoiesis in the liver and spleen;
- the gastrointestinal system (mainly in dogs); and,
- the testes (azoospermia with severe testicular atrophy) in rats and dogs, at all dose levels tested.

Most of the alterations were resolved by the end of the observation period, with exception of the testicular lesions, as expected due to the limited observation period.

During repeat-dose toxicity studies, unscheduled mortality was observed in one female rat at 3.5 mg/kg (21 mg/m², on Day 9) and two dogs (after the first drug administration at 0.6 and 0.8 m/kg [12 and 16 mg/m²]). In all cases moderate to marked immunosuppression (moderate to severe reticulopenia and thrombocytopenia), necrosis, hemorrhages in several organs (cervical lymph nodes, and/or spleen, liver, gastrointestinal tract, adrenals, thymus, and bone marrow) and thrombosis were considered the factors most likely contributory to the deaths of these animals.

Clinical chemistry evaluation in rats and dogs revealed changes in liver and kidney related parameters. These changes were of limited magnitude and not dose-related, without inter-parameter consistency (e.g., a three-fold increase in alkaline phosphatase and alanine aminotransferase, with 75 % decrease in aspartate aminotransferase) and lack of concurrent findings on the histopathology examination.

Injection site injury was sporadically noted in dogs and rats; thus, the irritating potential of PM060184 cannot be ruled out. The *in vitro* genotoxicity evaluation indicated mutagenic properties attributable to PM060184. No phototoxic potential for PM060184 is predicted from the *in vitro* experiment performed.

The MTDs calculated in two animal species either as single or repeated bolus administration are summarized in [Table 1](#).

Table 1. Maximum tolerated dose calculated for PM060184 in different animal species.

Species (Strain)	Gender	MTD mg/kg (mg/m ²)	
		Single-Dose	Repeat-Dose
Rat (Sprague-Dawley)	M	8.0 (48)	5.0 (30)
	F	4.0 (24)	2.0 (12)
Dog (Beagle)	M	0.8 (16)	0.4 (8)
	F	0.8 (16)	0.4 (8)

F, female; M, male; MTD, maximum tolerated dose.

According to the current data (MTD normalized by body surface area, mg/m²), the dog is slightly more sensitive than the rat to PM060184 following single administration; in the repeated dose studies, closer figures are seen in rats and dogs: MTD was determined as 30 and 12 mg/m² (5 and 2 mg/kg) for male and female rats, respectively, and 8 mg/m² (0.4 mg/kg) in dogs. Therefore, starting doses in patients are similarly predicted either by taking 1/10th of the lowest rat-derived MTD (1.2 mg/m²) or 1/6th of the dog-derived MTD (1.3 mg/m²).

In conclusion, the toxicology properties of PM060184 make the compound suitable for further evaluation in cancer patients. The major toxicities observed in animals (rats and dogs) are expected for chemotherapeutic agents, and can be adequately monitored by hematological, biochemical, and cardiac assessments during clinical development.

1.2.2 Clinical Data

Up to the cutoff date of the 30 September 2016, 113 patients had been treated and evaluated with PM060184 as single agent in the clinical development program at PharmaMar ([Table 2](#)). The phase I program includes two single-agent clinical trials and one combination clinical trial (assessing different schedules of administration in patients with solid tumors refractory to standard therapy or for which no standard therapy exists). Currently, one phase II clinical trial is evaluating the efficacy of PM060184 in advanced, hormone receptor positive, HER2 negative, breast carcinoma.

Table 2. Summary of the clinical program of PM060184.

Study	Schedule	Included patients ^a	Evaluated patients ^b	Status
Phase I trials				
PM60184-A-001-10	PM060184 10-min and 3-h infusions d1,8,15 q4wk	47	44	Completed
PM60184-A-002a-10	PM060184 10-min infusion d1,8 q3wk	38	38	Completed
PM60184-A-002b-10	PM060184 10-min infusion d1-3,15-17 q4wk	22	22	Ongoing
PM60184-A-003-14	Gemcitabine 30-min infusion/ PM060184 10-min infusion d1,8 q3wk	23	21	Ongoing
Phase II trials				
PM60184-B-001-15	PM060184 5- and 1-min infusions d1,8 q3wk . The 1-min i.v. administration was validated.	12 ^c	9	Ongoing
Total		142	134	

Cutoff date: 30 September 2016.

^a Patients registered in PharmaMar clinical database at cutoff, including patients not finally treated.

^b Patients treated and with available data in PharmaMar clinical database at cutoff.

^c Three patients were included but data were not available in the PharmaMar clinical database at cutoff.

d, day; min, minute; q3wk, every three weeks; q4wk, every four weeks.

To date, two phase I clinical trials have treated 104 solid tumor patients with different PM060184 schedules administered as single agent and as a 10-minute (min) i.v. administration: Days 1, 8 and 15 every four weeks (q4wk), Days 1 and 8 every three weeks (q3wk), and Days 1 to 3 and 15 to 17 every 28 days (q28d). The recommended dose (RD) has been established at 9.3 mg/m² for the Days 1 and 8 q3wk schedule. Most toxicities reported to date were mild to moderate, with peripheral motor/sensory neuropathy as the most frequent dose-limiting-toxicity (DLT), occurring in 6% of patients at doses above the RD.

As expected from a microtubule-binding agent, peripheral sensory neuropathy (PSN) was the principal dose-limiting toxicity. Fatigue, nausea/vomiting were also expected toxicities (but not dose-limiting). Hematological and biochemical abnormalities (regardless of relationship) did not represent a major safety concern.

Preliminary evidence of antitumor activity has been observed, four partial responses (PR) were reported in patients with cervix carcinoma, non-small cell lung cancer (NSCLC), breast and ovarian cancers, and 21 disease stabilizations (SDs) \geq 3 months in several tumor types. Thirteen evaluable CRC patients were treated and six (46%) had SD lasting three months or longer. Their median number of prior lines of chemotherapy for advanced or metastatic disease was three (range, 2–5) and median PFS was 4.7 months (range, 3.7–12.8 months).

Pharmacokinetics

Preliminary analysis of the integrated data available from clinical trials to date (three phase I and one phase II) has shown that the PK of PM060184 is characterized by:

- A wide distribution to peripheral tissues (195 L).
- Low inter-patient variability in CL and peripheral volume (V₂).
- A moderate to high total clearance (CL) (62.55 L/h).
- Distribution and elimination linearity at the dose levels explored.
- Negligible renal elimination.
- A clear effect between body surface area (BSA) and CL, weight and V₂.

1.3 STUDY RATIONALE

Systemic 5-FU-based chemotherapy produces meaningful improvements in median survival and PFS compared with BSC alone (7). These benefits are most pronounced with regimens containing [irinotecan](#) or [oxaliplatin](#) in combination with 5-FU, which represent the mainstay of advanced and metastatic CRC chemotherapy.

Consequently, when patients with advanced or metastatic CRC have received prior FP, irinotecan and oxaliplatin-based regimens (in addition to any ad hoc therapy targeting EGFR, and/or VEGF, according to tumor characteristics), clinical trials with investigational medicinal products (IMPs) are warranted.

PM060184 is a novel microtubule inhibitor (MTI), with a different, specific binding site on the β -tubulin, that is distinct from the vinca domain used by vinca alkaloids, as well as the taxane domain and binding site. PM060184 induces microtubule depolymerization (8) and caspase-dependent, as well as non-classical apoptosis pathways (9). PM060184 has shown *in vitro* and *in vivo* antitumor activity at nanomolar concentrations in CRC (10). Thirteen evaluable CRC patients were treated with single-

agent PM060184 to date and six (46%) had SD lasting three months or longer with a median PFS of 4.7 months (range, 3.7–12.8 months).

This trial will evaluate the efficacy of PM060184 in terms of progression-free survival at 12 weeks (PFS3) in advanced or metastatic CRC patients progressing after standard treatments (fluoropyrimidine, irinotecan, and oxaliplatin).

Patients in this trial will receive PM060184 as a 30-minute i.v. infusion on Days 1 and 8 q3wk. The dose selected (9.3 mg/m²) is the recommended dose for phase II studies that was determined for this same schedule, with PM060184 given as a 10-minute i.v. infusion, in study PM60184-A-002a-10 (see Section 1.2.2).

Metabolomic (Biomarkers) Study Rationale

Metabolomics (metabonomics/metabolomics), i.e., the determination of endogenous low-molecular-weight molecules or metabolites in a body fluid and their changes as a consequence of stimuli such as medical interventions, is currently being used to evaluate the efficacy and safety of medical interventions in cancer (11), thus allowing for the discovery of predictive biomarkers of drug response (12).

The metabolic profile of the patients before and after treatment with PM060184 will be compared to search for systematic variations that may serve as biomarkers of PK, safety and/or efficacy response to treatment with PM060184. Particular attention will be given to specific metabolic patterns observed in patients who develop peripheral neuropathy associated with PM060184. For this purpose, a blood sample will be collected prior to treatment administration on Day 1 and Day 8 of Cycle 1, and also on Day 8 of Cycle 2.

Pharmacogenomic/Pharmacogenetic Substudy Rationale

The rationale of the exploratory and optional substudy includes the evaluation of potential markers of sensitivity to PM060184 treatment with microtubule-interacting agents in a population of advanced CRC patients. These molecular markers would help in the future selection of patients who might preferentially benefit from PM060184 therapy, thus contributing to improved health care through a more individualized medicine.

There is growing evidence that the effects of tubulin-targeting drugs in endothelial cells are much more subtle than originally thought. In fact, some tubulin-binding drugs have been known to have antivasular (antiangiogenesis or vascular-disrupting) activities that can target abnormal tumor vessels (13, 14). PM060184 inhibits tubulin polymerization inducing alterations of the microtubule mass and dynamics, as well as the appearance of multipolar spindles. These effects will induce cell cycle arrest at G2/M. Cells will finally die by apoptosis or remain blocked in a multinucleated state. Thus, since PM060184 induces cytotoxicity by inhibiting tubulin polymerization, it is possible that alterations in β -tubulin isotype content and/or MAPs may alter sensitivity to this agent.

BRAF-mutant colon cancers have a characteristic gene expression signature that is also found in some tumors lacking this mutation: BRAF-like KRAS mutants and double wild-type patients have similarly poor prognosis. This suggests a common biology between these tumors and adds prognostic and biologic information that is not captured by the mutation classification alone (15).

These BRAF-like tumors represent 20% of colon cancers and have been shown to display far greater sensitivity to the microtubule poison, vinorelbine, and will also be explored by the genomic assays in the pharmacogenomic (PGx) substudy (16).

PM060184 is a very potent microtubule inhibitor; thus the sensitivity of this subset of patients, should sample size allow it, will be explored more specifically for potential differences.

Finally, a pharmacogenetic (PGt) analysis will explore factors that may help explain individual variability in the main PK parameters and safety outcomes, the presence or absence of germline mutations or polymorphisms will be analyzed in leukocyte DNA.

2. OVERALL STUDY DESIGN

This is a phase II, multicenter, open-label, study of single-agent PM060184 to evaluate efficacy in patients with advanced CRC progressing after standard therapy.

Initially, 24 patients who are evaluable for the primary endpoint will be included and a futility analysis will be performed (first stage). If at least seven of these patients achieve PFS3, then the study will proceed to a second stage and 36 additional patients will be recruited.

An exploratory substudy will address pharmacogenomic and pharmacogenetic objectives. All patients who participate in the PM60184-B-002-17 clinical trial will be eligible for the substudy if they voluntarily sign a separate informed consent (IC). Refusal to participate in the substudy will not affect a patient's participation in the clinical trial.

3. STUDY OBJECTIVES

Primary:

- To evaluate the efficacy of PM060184 in terms of progression-free survival at 12 weeks (PFS3) in patients with advanced CRC after standard therapy.

Secondary:

- To evaluate OS; PFS; overall response rate (ORR); and duration of response (DOR).
- To characterize the safety profile and feasibility of PM060184 in this population.
- To describe PN and quality of life (QoL) profiles in this population using patient-reported outcomes (PRO) as measured by the European Organisation for Research and Treatment of Cancer (EORTC) quality of life questionnaires (QLQ) for chemotherapy-induced peripheral neuropathy (QLQ-CIPN20) and general QoL (QLQ-C30).
- To characterize the PK of PM060184 in this population.
- To characterize the metabolomics of PM060184, i.e. PM060184, i.e., systemic variations in the patient's pre- and post-treatment metabolic profile that allow the identification of potential biomarkers of PK, safety and/or efficacy response to PM060184.
- To characterize PGt of PM060184 in this population by identifying the presence or absence of germline mutations or polymorphisms that may help explain individual variability in the main PK parameters and safety outcomes.
- To characterize PGx of PM060184 in this population by analyzing the potential predictive factors (including BRAF-mutant-like gene expression subtypes) of sensitivity/resistance to PM060184 treatment.

4. SELECTION OF PATIENTS

Patients with relapsed, metastatic/locally advanced CRC with any KRAS-mutation status (wild-type, mutated, or status unknown), progressing after standard treatments (fluoropyrimidine, irinotecan, and oxaliplatin).

4.1 INCLUSION CRITERIA

- 1) Voluntarily written informed consent, obtained before the beginning of any study-specific procedures.
- 2) Age \geq 18 years.
- 3) Histologically-cytologically documented adenocarcinoma of colon or rectum that has progressed to the last prior treatment before inclusion.
- 4) Measurable disease according to Response Evaluation Criteria in Solid Tumors (RECIST) v.1.1 (17). If the only tumor lesion is situated in a previously irradiated area or in an area subjected to other loco-regional therapy, progression in the lesion must be demonstrated radiologically.
- 5) Previous treatment in any setting with fluoropyrimidine, oxaliplatin and irinotecan in any combination (unless any is contraindicated).
 - a) Adjuvant chemotherapy-based treatments count as prior therapy, as long as relapse had occurred during or within six months of completion of such therapies.
 - b) Cumulative dose of prior oxaliplatin (if any) must be known.
 - c) Prior cetuximab, panitumumab, bevacizumab, aflibercept, and regorafenib are allowed.
- 6) No more than two prior therapies for metastatic disease.
- 7) Washout periods for prior therapies (defined in relation to planned start of study treatment [first dose administration]):
 - a) At least three weeks since the last administration of an antineoplastic treatment (chemotherapy, biological, targeted or investigational therapies).
 - b) At least three weeks since radiotherapy involving up to 35% of bone marrow (radiotherapy involving $>$ 35% of bone marrow is not allowed) or two weeks since the end of palliative radiotherapy including single doses (18).
 - c) At least four weeks since any major surgical procedure, open biopsy, or significant traumatic injury.
- 8) Eastern Cooperative Oncology Group (ECOG) performance status (PS) 0 or 1 (Appendix 1).
- 9) Life expectancy \geq 3 months.
- 10) Adequate bone marrow, liver, and kidney function:
 - a) Hemoglobin \geq 9 g/dL.
 - b) Absolute neutrophil count (ANC) \geq 1.5×10^9 /L.
 - c) Platelet count \geq 100×10^9 /L.
 - d) Serum creatinine \leq 1.5 mg/dL or calculated creatinine clearance \geq 40 mL/min (Cockcroft-Gault formula, Appendix 2).
 - e) Albumin \geq 2.5 g/dL.
 - f) Total serum bilirubin \leq 1.5 times the upper limit of normal (ULN), except in case of Gilbert syndrome.

g) Alanine aminotransferase (ALT) and aspartate aminotransferase (AST) $\leq 3 \times$ ULN ($\leq 5.0 \times$ ULN in the case of liver metastases).

- 11) Recovery to grade ≤ 1 from any toxicity due to previous therapy (including peripheral sensory/motor neuropathy but excluding alopecia).
- 12) Left ventricular ejection fraction (LVEF) by echocardiography (ECHO) or multiple-gated acquisition (MUGA) scan within normal range (according to institutional standards).
- 13) Evidence of non-childbearing status for women of childbearing potential (WOCBP). WOCBP must agree to use a highly effective contraceptive measure during the trial and up to six months after treatment discontinuation, and fertile male patients must agree to refrain from fathering a child or donating sperm during the trial and up to four months after treatment discontinuation.*

* Valid methods to determine the childbearing potential, adequate contraception and requirements for WOCBP partners are described in [Appendix 3](#).

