5.3 CRITERIA FOR TREATMENT CONTINUATION

Patients will be treated with additional cycles of PM060184 until disease progression (PD), as long as none of the following occur: unacceptable toxicity, and/or patient refusal to receive further study treatment, and/or Investigators’ decision.

The administration of subsequent cycles (after Cycle 1) should be delayed if criteria for treatment continuation ([Table 4](#)) are not met on the corresponding Day 1. If criteria for treatment continuation are not met on Day 8 (i.e. seven days after the first dose administration of a cycle) of any cycle, administration should be omitted instead of delayed.

Table 4. Criteria for treatment continuation.

Abnormality	Day 1 ^a	Day 8
ANC	$\geq 1.5 \times 10^9/L$	$\geq 1.0 \times 10^9/L$
Platelets	$\geq 100 \times 10^9/L$	$\geq 75 \times 10^9/L$
Hemoglobin ^b	≥ 9 g/dL	≥ 9 g/dL
Total bilirubin	$\leq 1.5 \times$ ULN (grade 1)	
AST/ALT	Grade ≤ 1 ^c	Grade ≤ 2
Calculated CrCL (Cockcroft-Gault formula)	≥ 40 mL/min	≥ 30 mL/min
Peripheral sensory/motor neuropathy	Grade ≤ 2	Grade ≤ 2
Nausea/vomiting, fatigue, anorexia	Grade ≤ 2	Grade ≤ 2
Other non-hematological drug-related AEs (except metabolic abnormalities ^d)	Grade ≤ 1	Grade ≤ 2

^a Except Day 1 of Cycle 1.

^b If hemoglobin levels are not met, the Investigator will have the option of giving the patient a transfusion instead of delaying (on Day 1) or omitting (on Day 8) a dose.

^c Grade ≤ 2 , for patients with liver metastases and with AST and/or ALT levels $\leq 5.0 \times$ ULN at registration.

^d Any grade accepted for increased GGT. Up to grade 4 accepted for non-symptomatic metabolic abnormalities (e.g., sodium, magnesium, potassium, calcium).

AE, adverse event; ALT, alanine aminotransferase; ANC, absolute neutrophil count; AST, aspartate aminotransferase; CrCL, creatinine clearance; GGT, gamma-glutamyltransferase; ULN, upper limit of normal.

A maximum delay of 15 days is allowed for the recovery of patients from toxicity. If toxicities have not recovered after this period, the patient should discontinue treatment. Exceptionally, in case of obvious clinical benefit, the patient can remain on treatment but only after discussion and mutual agreement with the Sponsor, and upon recovery of all parameters according to the aforementioned criteria.

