6.3.2 Reasons For Treatment Discontinuation

Patients will receive study treatment while it is considered to be in their best interest or until study termination. Specifically, treatment will continue until:

- Disease progression.
- Unacceptable toxicity (including any toxicity leading to the need for a third dose reduction or severe hypersensitivity reactions, except in the case of obvious clinical benefit, in which event the patient could be allowed to remain on treatment once agreed with the Sponsor).
- Patient refusal to receive further study treatment and/or non-compliance with study requirements.
- Intercurrent serious illness.
- Pregnancy.
- Investigator's decision.
- Protocol deviation with an effect on the risk/benefit ratio of the clinical trial.
- PM060184 treatment delay > 15 days from the due date (except in case of clear clinical benefit and with the Sponsor's approval).
- Clinical cutoff. Patients who have not progressed at these time points could be treated in a compassionate use program (according to country regulations).

Patients who are withdrawn for any reasons must not be re-treated in the context of this study at any time. For follow-up activities, please refer to Section [7.6](#).

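### Entry accepts serum creatinine alone, but re-treatment requires a calculated creatinine clearance, so some eligible patients fail the continuation criteria with unchanged renal values

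*Protocol*

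**What the plan says.** **Entry.** Protocol 4.1, criterion 10(d), and its synopsis copy set the renal limit as serum creatinine of at most "1.5 mg/dL or calculated creatinine clearance" of at least 40 mL/min by Cockcroft-Gault. Meeting either limb is sufficient.

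**Re-treatment.** In Table 4 of Protocol 5.3 (synopsis Table 2) the renal row begins "Calculated CrCL (Cockcroft-Gault formula" and sets at least 40 mL/min for Day 1 and at least 30 mL/min for Day 8. Serum creatinine does not appear. The Day 1 column carries the footnote "Except Day 1 of Cycle 1", so it first applies at Cycle 2. The Day 8 column has no such exemption and applies from Cycle 1.

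**Consequence of failing.** A missed Day 8 criterion means that the dose is omitted. For Day 1: "The administration of subsequent cycles (after Cycle 1) should be delayed if criteria for treatment continuation" are not met. Section 5.3 continues "A maximum delay of 15 days is allowed for the recovery of patients from toxicity" and "If toxicities have not recovered after this period, the patient should discontinue treatment". It lets a patient with obvious benefit stay on by agreement with the sponsor, but only "upon recovery of all parameters according to the aforementioned criteria". Section 6.3.2 lists a delay of more than 15 days as a reason to stop, "except in case of clear clinical benefit and with the Sponsor's approval", and there the recovery condition is not repeated.

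**The concern.** The entry rule and the re-treatment rule use the same figure of 40 mL/min, but only the entry rule lets creatinine stand in for it. A patient admitted on creatinine alone can therefore be acceptable for the first dose and unacceptable for Cycle 2 on identical laboratory values.

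The patient would be exposed to one or two doses and then meet a barrier that was already visible at screening, where Table 8 of Protocol 7.1 has the clearance calculated. In the data, the stop would be due neither to progression nor to toxicity. The patient's place in the primary analysis would then turn on the evaluability and replacement rules instead of on a planned course of treatment.

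**Working it through.** There is no planned figure to reproduce here. The check applies the protocol's own formula to patients who satisfy 10(d) through creatinine.

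**Inputs from the documents.** Creatinine limit 1.5 mg/dL (4.1); clearance limits 40 mL/min on Day 1 and 30 mL/min on Day 8 (Table 4); formula from Appendix 2:

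CrCL = (140 − age) × weight / (72 × creatinine), multiplied by 0.85 for women.

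**Assumptions.** Age, weight, sex and creatinine in the examples are illustrative. The only age figure in the documents is a median of 68 years at diagnosis (Protocol 1.1), which describes colorectal cancer in general and not this trial's population.

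| Assumed patient (all meet 10(d)) | Calculation | CrCL, mL/min | Cycle 1 Day 8 (≥ 30) | Cycle 2 Day 1 (≥ 40) |
|---|---|---|---|---|
| Woman 70 y, 55 kg, 1.5 mg/dL | 70 × 55 / 108 × 0.85 | 30.3 | passes | fails |
| Man 75 y, 60 kg, 1.5 mg/dL | 65 × 60 / 108 | 36.1 | passes | fails |
| Woman 75 y, 55 kg, 1.2 mg/dL | 65 × 55 / 86.4 × 0.85 | 35.2 | passes | fails |
| Woman 80 y, 50 kg, 1.3 mg/dL | 60 × 50 / 93.6 × 0.85 | 27.2 | fails | fails |
| Woman 68 y, 70 kg, 1.5 mg/dL | 72 × 70 / 108 × 0.85 | 39.7 | passes | fails |
| Man 68 y, 70 kg, 1.5 mg/dL | 72 × 70 / 108 | 46.7 | passes | passes |
| Woman 75 y, 60 kg, 1.0 mg/dL | 65 × 60 / 72 × 0.85 | 46.0 | passes | passes |

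**Range at the entry ceiling of 1.5 mg/dL.** Clearance is below 40 when (140 − age) × weight is below 40 × 72 × 1.5 = 4320 for men, or 4320 / 0.85 = 5082 for women. The age above which this happens is:

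| Weight | Men | Women |
|---|---|---|
| 50 kg | 53.6 y | 38.4 y |
| 60 kg | 68.0 y | 55.3 y |
| 70 kg | 78.3 y | 67.4 y |
| 80 kg | 86.0 y | 76.5 y |

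At lower creatinine the affected group shrinks, as the last row of the first table shows.

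**What then happens to the patient.**

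1. Clearance from 30 to below 40: both Cycle 1 doses can be given and Cycle 2 is delayed. Cycle 2 Day 1 is planned for Day 22, so a 15-day delay ends at Day 22 + 15 = Day 37. The first scheduled tumor assessment is at Week 6, with a window that only runs later, so it falls after Day 37. Clear clinical benefit, which the 6.3.2 exception needs, would be hard to show by then.
2. Clearance below 30: Day 8 of Cycle 1 is also omitted, which leaves one dose.

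**What then happens in the analysis** (Protocol 6.3.4 and 8.1, mirrored in SAP section 4).

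1. A one-dose patient falls short of the minimum treatment and is replaced whatever the Week 12 scan shows. The exception is a patient who progresses before Week 12, whom 8.1 makes an evaluable non-responder.
2. A patient with a complete first cycle is a non-responder on progression before Week 12. Without progression, the patient is counted if assessed as 8.1 requires, and replaced if the Week 12 assessment is missing.
3. An unchanged clearance is neither a treatment-related event nor unmanageable toxicity, so the stop itself does not place the patient in a non-responder category.

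**The case against.** **The two rules govern different decisions.** A reader might infer that the sections contradict each other. They do not strictly do so: 10(d) decides entry, Table 4 decides re-dosing, and the Cycle 1 Day 1 footnote separates the two. Limits differ elsewhere as well; neuropathy must be grade 1 or less to enter and grade 2 or less to continue. Both renal rules can be followed as written. That objection stands, and the accurate word is mismatch. It still looks unintended. The Day 1 clearance limit repeats the entry figure without its alternative, and Table 4 makes a baseline-related allowance for AST/ALT in patients with liver metastases but none for clearance.

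**Safeguards exist before the first dose.** Clearance is calculated at screening, the sponsor must agree to registration (7.2), and exclusion 4(g) covers known active renal disease. These may catch some patients. All are discretionary or partial, and none sets a clearance floor. The re-check of eligibility before treatment does not help either, because creatinine alone still satisfies 10(d).

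**Stopping is not automatic.** A reader might infer from 5.3 that the patient must stop. The sentence there speaks of toxicities that have not recovered, and an unchanged baseline value is not a toxicity. The rule that fits is the delay of more than 15 days in 6.3.2, which carries an exception. The objection is right on the text, although the timing leaves that exception little practical room.

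**The examples are chosen.** Several combine low weight with creatinine at or near the ceiling. This is also fair. Protocol 1.2.2 reports negligible renal elimination, and no safety hazard is claimed here beyond avoidable exposure and a curtailed course.

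**Conclusion.** The point holds as a mismatch: for a subset of eligible patients the re-treatment rule is stricter than the entry rule, so unchanged renal values pass one and fail the other. The arithmetic follows directly from Appendix 2. It affects some older, lighter and more often female patients, mostly with creatinine toward the upper end of the permitted range.

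The number affected is unknown. The documents give no baseline distribution of creatinine, weight or sex, and it may be small or nil. A reader might also infer damage to power or to the decision rule of 25 successes in 60. The documents do not support that: non-evaluable patients are replaced until 60 are evaluable, and nothing allows the share affected to be estimated. What remains is a predictable stop after one or two doses for certain patients, and an avoidable dependence of their status on the evaluability rules. That is worth correcting, but it does not undermine the design.

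**What to change.** Reconcile criterion 10(d) in Protocol 4.1 and its synopsis copy with the clearance row of Table 4 in 5.3 and synopsis Table 2, so that an unchanged renal value gives a consistent answer at entry and at re-treatment. The sponsor's medical team decides which rule stands; this review takes no position on the limit. While the text is open, the exceptions to the 15-day limit in 5.3 and 6.3.2 should also be reconciled, since only the former requires recovery.

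The cost is protocol wording in a few places and their synopsis copies. The SAP does not restate the renal limits, and neither the sample size nor the analysis changes.
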